4.2 Exclusion Criteria

In order to participate in this study, a subject MUST NOT:

1. Be a female who is pregnant, nursing, or of childbearing potential while not practicing effective contraceptive methods. Female subjects must undergo a blood or urine pregnancy test at screening and within 36 hours prior to infusion.
2. Inability to perform any of the assessments required for endpoint analysis.
3. Active listing (or expected future listing) for transplant of any organ.
4. Clinically important abnormal screening laboratory values, including but not limited to: hemoglobin <8 g/dl, white blood cell count <3000/mm³, platelets <80,000/mm³, INR > 1.5 not due to a reversible cause (i.e. Coumadin), aspartate transaminase, alanine transaminase, or alkaline phosphatase > 3 times upper limit of normal.
5. Serious comorbid illness that, in the opinion of the investigator, may compromise the safety or compliance of the subject or preclude successful completion of the study. Including, but not limited to: HIV, advanced liver or renal failure, class III/IV congestive heart failure, myocardial infarction, unstable angina, or cardiac revascularization within the last six months, or severe obstructive ventilatory defect.
6. Have known allergies to penicillin or streptomycin.
7. Be a solid organ transplant recipient. This does not include prior cell-based therapy (>12 months prior enrollment) bone, skin, ligament, tendon or corneal grafting. Have a history of organ or cell transplant rejection.
8. Have a clinical history of malignancy within 3 years (i.e., subjects with prior malignancy must be disease free for 3 years), except curatively-treated basal cell carcinoma, squamous cell carcinoma, melanoma in situ or cervical carcinoma, if recurrence occurs.
9. Have a non-pulmonary condition that limits lifespan to < 1 year.
10. History of drug abuse (illegal "street" drugs except marijuana, or prescription medications not being used appropriately for a pre-existing medical condition) or alcohol abuse (\geq 5 drinks/day for > 3 months), or documented medical, occupational, or legal problems arising from the use of alcohol or drugs within the past 24 months
11. Be serum positive for HIV, hepatitis BsAg or Viremic hepatitis C, and/or Syphilis – VDRL (If VDRL is reactive Confirmation with FTA-ABS is needed (Syphilis)).
12. Be currently participating (or participated within the previous 30 days) in an investigational therapeutic or device trial.
13. Patients with EF<45% (heart failure patients).

14. GFR \leq 35 (chronic kidney disease stage 3 or higher).
15. Liver disease (elevated LFTs greater than 3x upper limit of normal).
16. Advanced pulmonary disease (requiring home oxygen and/or less than 1 expected life span).
17. Proliferative diabetic retinopathy if history of diabetes
18. Hemoglobin A1C greater than 7.

4.3 Concomitant Treatments, Procedures, and Nondrug Therapies

Subjects will receive standard-of-care medical management of metabolic syndrome, as recommended by the ATP III, American Heart Association (AHA) and the National Institutes of Health (NIH), and the Endocrine Society. All concomitant medications (prescription or over-the counter) as well as procedures or nondrug therapies (e.g. continuous positive airway pressure, pulmonary rehabilitation) will be recorded at the initial screening visit and updated at each subsequent visit.

4.4 Withdrawal Criteria

Subjects will be informed that they have the right to withdraw from the study at any time and for any reason without prejudice to future or continued medical care. Subjects must be withdrawn for the following reasons:

- Subject request.
- Subject is unable or unwilling to comply with the protocol.
- Medical reasons, at the discretion of the investigator.

Reason for withdrawal will be recorded in the subject's case report form. In order to adequately monitor for safety and potential efficacy outcomes, subjects who are withdrawn for any reason after receiving the first infusion should be encouraged to return for all assessments through the end of the study period. All efforts should be made to continue to record safety data and lung function parameters for all withdrawn subjects. Subjects who withdraw for reasons unrelated to the study or study drug (e.g. withdrawal of consent or loss to follow-up) may be replaced if deemed necessary to meet study objectives. Replacement subjects will be assigned unique identification numbers.

5. MESENCHYMAL STEM CELL DONORS

The availability of allogeneic BMMSCs offers the potential for an "off the shelf" product for subjects. Significant data has been generated to demonstrate that the allogeneic BMMSCs are immune-privileged and can be infused without immune rejection despite disparate HLA phenotypes.

Screening of allogeneic donors will follow standard transplant practices and all allogeneic donors will meet allogeneic donor eligibility criteria as outlined in 21 CFR Part 1271.

Allogeneic donor testing will include anti-HIV-1/2, anti-HTLV I/II, anti-HCV, HIV-1 nucleic acid testing, HCV nucleic acid testing, HBsAg, anti-HBc(IgG and IgM), CMV, West Nile Virus nucleic acid, *T. cruzi* ELISA (Chagas), Zika virus, Syphilis – VDRL (Confirmation with FTA-ABS if needed (Syphilis)) and RPR. Potential donors testing positive for any of these infectious diseases with the exception of CMV, will be ineligible. Bone marrow aspirates will be obtained from normal individuals and BMMSCs will be isolated and expanded.

5.1 Bone Marrow Aspiration, cord tissue harvest, MSC culture for generation of MSCs and Placebo formulation.

A total of approximately 60ml to 120ml of BM will be obtained from a healthy donor's bone marrow. BM will be aspirated from the posterior iliac crest into heparinized syringes. The mononuclear cell fraction will be isolated using a density gradient with Lymphocyte Separation Media (specific gravity 1.077). The low-density cells will be collected and washed with Plasma-LyteA containing 1% HSA. The washed cells will be sampled and viable cell numbers determined. The MNCs will be prepared with antibiotic (ie. penicillin or streptomycin). The BM mononuclear cells will be seeded into 175 cm² tissue culture flasks in alpha MEM containing 20% FBS. After 14 days of culture, passage zero (P0) cells will be harvested by trypsin treatment and expanded into 60 flasks. After 7 to 10 days P1 cells are harvested by trypsin treatment (P1 cells). Cells from P1 will be cultured for 7 to 10 days and harvested by trypsin treatment and expanded into 180 flasks (P2 cells) with the option of expanding them once again, to P3. After 7-10 days P3 cells would be harvested by trypsin treatment and cryopreserved.

Before consenting and collecting the umbilical cord tissue, the maternal blood will be screened for infectious disease.

Collection of Umbilical Cord Tissue: The cord will be clamped then cut and 6 to 15 cm of the cord will be transferred into a labeled container containing the collection media supplemented with antibiotics. A specialized validated temperature controlled container (2-15°C) will be used. The collection kit with the cord will be transported to the processing facility within 36 hrs. Upon arrival at the processing facility, the sample will be assigned a unique ID that enables the unit to be tracked throughout the process.

The umbilical cord tissue will be enzymatically digested. The digested cells will be washed and cultured. An expansion process of 3 passages will take place followed by cryopreservation.

Placebo will be formulated as following:

The placebo group will receive infusion of PlasmaLyte-A supplemented with 1% HSA. The placebo product will undergo QC testing before injection for gram stain and endotoxin. The sterility (aerobic, anaerobic and fungal) samples will be taken from final product and cultured for 14 days. Product will only be released if testing meets following criteria:

Gram Stain – Negative

Endotoxin - < 5EU/kg/hr.

5.2 Donor Eligibility

5.2.1 Bone Marrow Donors Screening and Testing

Donors (male or female) between the ages of 18 to 45 (inclusive) will be screened as potential BM donors. Donors will be evaluated by history and physical examination. The history will include:

- History of malignancy
- Bleeding abnormalities
- Prior deep venous thrombosis
- Known cardiac or pulmonary conditions
- Prior blood transfusions
- Vaccinations
- Questions to identify persons at risk of infectious disease transmission, including Zika virus
- Questions to identify persons at risk of transmitting hematological or immunological disease
- A physician will administer the National Marrow Donor Program (NMDP) Questionnaire (a donor health history screening questionnaire).

a. The physical examination will include evaluation for potential risks associated with the BM aspiration procedure. Prospective donors will have infectious disease testing including:

- Hepatitis B surface antigen (HBsAg)
- Hepatitis B core antibody (HBcAb)
- Hepatitis C virus antibody (HCV Ab)
- Human Immunodeficiency Virus (HIV) antibody (HIV 1/2)
- Cytomegalovirus antibody (CMV)
- HCV/HIV Nucleic Acid test
- West Nile Virus Nucleic Acid test
- Rapid Plasma Reagins (RPR) or VDRL (if VDRL reactive confirmation with FTA-ABS is needed (Syphilis))
- Human T-lymphotropic Virus I/II (HTLV I/II)
- *T. cruzi* ELISA test (Chagas disease)
- Zika Virus testing (RNA qualitative Real Time RT-PCR, Serum/Urine or Zika Virus Antibody (IgM), MAC-ELISA)

If a donor tests positive for CMV the donor may still be able to participate.

b. Prospective donors will also have the following tests:

- Complete blood count with differential
- Complete metabolic panel, magnesium, calcium, and uric acid
- Urinalysis
- Serum pregnancy test (Female only)

c. Eligibility Criteria for Normal Donors will include:

- Male and female gender
- No history of malignancy
- No active coagulopathy and/or hypocoagulable state
- No history of cardio/pulmonary conditions
- Negative tests for Hepatitis B, Hepatitis C, RPR or VDRL, Chagas, HIV 1, 2, HTLV I/II and NAT for HCV, HIV, Zika Virus and WNV.
- Hemoglobin \geq 13.0 g/dL if male; and if female donor hemoglobin \geq 11.0 g/dL
- Platelet count 140,000 to 440,000/ul
- WBC 3.0 to 11.0 K/ul
- No anomalies on the CBC and differential suggestive of a hematopoietic disorder or infection
- Creatinine \leq 1.5 mg/dL
- ALT \leq 112 IU/L
- Bilirubin $<$ 1.5 mg/dL
- No diabetes
- Systolic blood pressure \leq 170
- Diastolic blood pressure \leq 90
- No history of autoimmune disorders
- Negative serum or urine pregnancy test for female donors
- Body Mass Index (BMI) \leq 30

Female donors would need to be screened for pregnancy as the procedure may be an added risk to a fetus.

5.2.2 Umbilical Cord Tissue Donor Screening and Testing

Upon consent the maternal blood will be screened for infectious disease prior to collecting the umbilical cord tissue. This will prevent the introduction, transmission, and spread of communicable disease agents and diseases.

All Umbilical cord tissue donors between the ages of 18 to 35 must be tested and screened for the following:

- a. Donor screening and reviewing of relevant medical history records and social history for risk factors will be evaluated by history and physical examination. The history will include:
 - History of malignancy

- Bleeding abnormalities
- Prior deep venous thrombosis
- Known cardiac or pulmonary conditions
- Prior blood transfusions
- Vaccinations
- Questions to identify persons at risks of infectious disease transmission
- Questions to identify persons at risk of transmitting hematological or immunological disease

b. Umbilical donors are tested for transmissible infectious diseases as follow (results from any viral or infections agent testing must be negative):

- Hepatitis B surface antigen (HBsAg)
- Hepatitis B core antibody (HBcAb)
- Hepatitis C virus antibody (HCV Ab)
- Human Immunodeficiency Virus (HIV) antibody (HIV 1,2)
- Cytomegalovirus antibody (CMV) Immune Screen (total immunoglobulin, including IgG and IgM). Positive samples are tested for CMV DNA.
- HCV/HIV Nucleic Acid test
- West Nile Virus Nucleic Acid test
- Rapid Plasma Reagins (RPR)
- Human T-lymphotropic Virus I/II (HTLV I/II)
- *T. cruzi* ELISA test (Chagas disease)
- Zika Virus Testing
- VDRL (confirmation with FTA-ABS if needed (Syphilis))

Results from any viral or infectious agent testing must be negative.

c. Eligibility Criteria for Umbilical Donors will also include:

- Female gender
- No history of malignancy
- Cancer
- Bleeding abnormalities
- Neurological diseases
- Blood and bleeding disorders, including sickle cell disease
- History of autoimmune disorders
- No family history (biologic mother, father or sibling) of genetic disorder that may affect the recipient.
- Negative tests for Hepatitis B, Hepatitis C, RPR, VDRL, Chagas, HIV 1/2, HTLV I/II and NAT for HCV, HIV, Zika Virus and West Nile Virus.
- No diabetes (gestational diabetes is not an exclusion criteria)

5.3 Bone Marrow Donor Consent

Informed consent will be obtained from all potential donors. The procedure will be explained in terms the donor can understand, and will include information about the significant risks of the procedure. Potential donors will have an opportunity to ask questions, and the right to refuse or withdraw consent, and access to the results of all tests.

Donors will need to have virology's redrawn if BMA procedure not completed 7 days from the initial virology results.

5.4 Follow-up Schedule for Bone Marrow Donors

After discharge from the hospital, the bone marrow donor will be contacted by the study team with a follow-up telephone call to determine the well-being, health status of the donor and/or if any adverse events have occurred. Attempts should be made to follow-up via phone within a week of the BMA procedure. The donor will be provided with contact telephone numbers in the consent form for any questions or comments.

5.5 Biomarker Assessment for Bone Marrow Donors

A separate blood sample of about 10mL will be obtained at the donation visit for gene expression profiling. All samples will be identified so that they can be linked to individual subjects. These samples may be stored indefinitely. Individual results will not be returned to the subject or the study physician. The samples will be linked to subjects, but there will be no recontact. Data presented in publications will not contain individual subjects' gene expression or clinical characteristics or outcomes; only aggregate data from the entire study will be disclosed.

6. TREATMENT OF SUBJECTS

6.1 Study Investigational Product

The investigational product (IP) consists of BMMSCs obtained from donor bone marrow. Screening of allogeneic donors will follow standard transplant practices and all allogeneic donors will meet allogeneic donor eligibility criteria as outlined in 21 CFR Part 1271.

The investigational product (IP) consists of UCMSCs obtained from donor cord tissue. Screening of allogeneic donors will follow standard transplant practices and all allogeneic donors will meet allogeneic donor eligibility criteria as outlined in 21 CFR Part 1271. Cord tissue will be obtained from normal donors.

6.2 Dosing

The allogeneic BMMSCs or UCMSCs will be derived from normal donors meeting criteria for allogeneic unrelated human bone marrow stem cell source or human cord tissue manufactured by the ISCI Clinical Research Cell Manufacturing facility at the University of Miami.

6.3 Dosage Rationale

A safety profile for IV infusion of BMMSCs and UCMSCs is based on results from previous completed toxicology results⁷⁶. The results from previous studies demonstrate that the product can be administered intravenously without toxic events at up to 65×10^6 hMSC/kg dose delivered in one bolus infusion or at 100×10^6 hMSC/kg cumulative dose delivered by 5 infusions (20×10^6 hMSC/kg per infusion).

The evidence supports the conclusion that it is feasible to dose subjects in this study based on a standard dose of hMSCs rather than per kilogram of body weight. The total cell number corresponds to a range of $1.3 - 4.4 \times 10^6$ hMSCs per kg per infusion for subjects with 45 to 150kg body weight.

Therefore, results from previous trials support the rationale on the safety and potential efficacy of the selected maximum dose of 100×10^6 allo-hMSCs.

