Three (3) subjects will be treated with a single administration of 2×10^7 (20 million) UCMSCs delivered via peripheral intravenous infusion.

Group 2 (3 subjects)

Three (3) subjects will be treated with a single IV administration of 2×10^7 (20 million) BMMSCs delivered via peripheral intravenous infusion.

The subjects in the high dose (Groups 3 & 4) will not be treated until the subjects in the low dose (Groups 1 & 2) have completed their one-month follow-up assessments and safety measures have been reviewed to confirm that there have been no treatment emergent SAE's.

Group 3 (3 subjects)

Three (3) subjects will be treated with a single IV administration of 1×10^8 (100 million) UCMSCs delivered via peripheral intravenous infusion.

Group 4 (3 subjects)

Three (3) subjects will be treated with a single IV administration of 1×10^8 (100 million) BMMSCs delivered via peripheral intravenous infusion.

Randomized Phase (30 subjects)

Group A (10 subjects – UCMSCs)

Ten (10) subjects will be treated with a single administration of 1×10^8 (100 million) UCMSCs delivered via peripheral intravenous infusion.

Group B (10 subjects – BMMSCs)

Ten (10) subjects will be treated with a single administration of 1×10^8 (100 million) BMMSC delivered via peripheral intravenous infusion.

Group C (10 subjects – Placebo)

Ten (10) subjects will be treated with a single administration of placebo delivered via peripheral intravenous infusion.

Subjects in each pilot phase group (Group 1, 2, 3 and 4) will not be treated less than 5 days apart.

The randomized portion of the study will be conducted after a full review of the safety data from the Pilot Phase by the DSMB

Patients will be randomized in a 1:1:1:1 ratio to one of the 3 groups in the randomized phase. For subjects randomized to B (BMMSCs); the cells will be derived from a healthy allogeneic bone marrow donor (obtained by iliac crest aspiration).

For subjects randomized to Group A (UCMSCs); the cells will be derived from a healthy allogeneic umbilical cord tissue donor.

Route of Administration	Peripheral Intravenous Infusion
Duration of Study Participation	12 months (Follow-up will be at 2 weeks, 1 Month, 3, 6, and 12 months.)
Inclusion Criteria	
1. Provide written informed consent2. Subjects age ≥ 21 and ≤ 95 years at the time of signing the Informed Consent Form.3. Each subject must have endothelial dysfunction. Endothelial dysfunction Criteria:

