1.6.2 MSCs Efficacy in Graft Versus Host Disease (GVHD)

In a phase II trial for treating acute GVHD, 55 patients received between 1 or more intravenous infusions of 1.4×10^6 allogenic MSCs/kg body mass (median dose)³⁵. Twenty-seven (27) patients received one dose, 22 received two doses, and 6 received 3-5 doses. The MSCs were obtained from HLA-identical sibling donors ($n=5$), haploidentical donors ($n=18$), or HLA-mismatched donors ($n=69$). Thirty (30) of the patients had a complete response, and improvement was seen in a further 9 patients. The complete responders had significantly higher 1-year and 2-year survival rate. Furthermore, the response rates were not associated with HLA-matching.

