Allogeneic MSC infusion has also been studied in a phase II trial of MSCs for the treatment of severe acute graft versus host disease⁶⁸. In this study, 55 subjects received 1-5 intravenous infusions of 1.4×10^6 cells/kg body weight from HLA matched and mismatched donors. A complete response was seen in 30 subjects and improvement was seen in 9

patients. Of note, response rates were not associated with HLA-matching. No infusion related side effects were noted and no long term adverse events were observed.

The safety and efficacy of allogeneic MSCs for the treatment of refractory lupus has also been explored¹¹⁹. Fifteen subjects received a single intravenous infusion of 1×10^6 cells/kg body weight. MSCs were derived from family members but were not HLA-matched. At 12 months, all subjects had improvement in disease activity as measured by 24-hour proteinuria (decreased from 2505.0 ± 1323.9 to 858.0 ± 800.7 mg/24hr, $p < 0.05$) and SLE Disease Activity Index scores (decreased from 12.2 ± 3.3 to 3.2 ± 2.8 , $p < 0.05$). No serious adverse events were noted in any of the subjects.

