3.2. RANDOMIZATION STUDY

This Phase I/II, randomized, blinded, placebo-controlled study is designed to evaluate the safety and tolerability of UCMSCs versus BMMSCs in subjects with chronic inflammation due to the metabolic syndrome and to explore potential efficacy at baseline, 3 and 6 months.

In the randomized phase of the trial, product will be prepared by ISCI GMP laboratory personnel. The selected personnel will not have contact with the investigators or subjects for this trial. At the time of administration, opaque tubing will be used to maintain double blinding. Treatments will be administered once and will consist of 1×10^8 (100 million) UCMSCs, 1×10^8 (100 million) BMMSCs or placebo. After each infusion, subjects will be monitored for immediate complications.

Continued safety and tolerability with review of adverse events (AEs) will be monitored at each visit. Efficacy parameters (6MWT and QOL questionnaires) will be assessed at various study visits. Clinical laboratory tests to assess safety will be performed at every clinic visit, excluding the baseline visit.

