6.4 Administration Rate

Prior clinical trials have used rates up to 30×10^6 hMSC/min where no infusion related toxicity was observed.

In the proposed study, the cell dose to be delivered is 20 or 100 million cells in 80 mL Cells will be delivered at a rate of 2mL/min, and delivered at a maximum rate of 2.5×10^6 hMSC/minute and will last approximately 40 minutes for both doses.

The infusion bag will be flushed with an additional 25 ml of 0.9% normal saline at the completion of allo-hMSC infusion and delivered at a rate of 2ml/min.

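### Does the per-kilogram range in section 6.3, about twice what 100 million cells gives, call for a change to the plan?

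*Combined protocol and SAP*

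**What the plan says.** Section 6.3 (Dosage Rationale) argues for giving each subject in this study a fixed number of cells, whatever the body weight. It then converts the total to 1.3 to 4.4 million "hMSCs per kg per infusion for subjects with 45 to 150kg body weight". Its last sentence states that "results from previous trials support the rationale on the safety and potential efficacy of the selected maximum dose" of 100 million cells. Earlier in the section, toxicology work is cited as showing no toxic events up to 65 million cells per kg in a single bolus.

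The cell numbers are also stated in three other places:

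- The Protocol Synopsis gives 20 million cells to pilot Groups 1 and 2, and 100 million to pilot Groups 3 and 4 and to randomized Groups A and B.
- Section 3.2 gives one administration of 100 million cells of either type, or placebo, in the randomized phase.
- Section 6.4 (Administration Rate) says "the cell dose to be delivered is 20 or 100 million cells in 80 mL", run at 2 mL/min with a maximum of 2.5 million "hMSC/minute and will last approximately 40 minutes for both doses".

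**The concern.** The conversion is a single division, and it does not give the printed answer. A reader who takes the range at face value would believe that subjects receive about twice as many cells per kilogram as the stated maximum provides. The sentence sits in the section that justifies the dose, where an ethics committee, the DSMB or a regulator would look.

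Much of the human experience cited in the introduction is expressed per kilogram. Section 1.6.2 gives 1.4 million "allogenic MSCs/kg body mass (median dose") in graft-versus-host disease. Section 1.8 reports a lupus study in which "Fifteen subjects received a single intravenous infusion of" 1 million cells per kg. If the per-kilogram figure for this trial is off by a factor of two, a comparison with those studies is off by the same factor. At worst, the mismatch could mean that the intended dose itself is in doubt.

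**Working it through.** **Inputs.** Printed range 1.3 to 4.4 million/kg, weights 45 to 150 kg, maximum 100 million cells, toxicology level 65 million/kg (all section 6.3). Study doses 20 and 100 million cells, 80 mL, 2 mL/min, 2.5 million cells/min (section 6.4).

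**Step 1: try to reproduce the printed range.** Cells per kg = total cells / weight.

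| Total cells | At 150 kg | At 45 kg |
|---|---|---|
| 20 million | 20/150 = 0.13 million/kg | 20/45 = 0.44 million/kg |
| 100 million | 100/150 = 0.67 million/kg | 100/45 = 2.22 million/kg |
| 200 million | 200/150 = 1.33 million/kg | 200/45 = 4.44 million/kg |

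Neither study dose gives 1.3 to 4.4 million/kg. A total of 200 million does, after rounding.

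**Step 2: back-calculate.** 1.3 × 150 = 195 million; 4.4 × 45 = 198 million. Both ends point to nearly the same total, so one misprinted digit is an unlikely explanation. Holding the dose at 100 million instead, the printed range would need weights of 100/4.4 = 23 kg to 100/1.3 = 77 kg.

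**Step 3: size.** Relative to 100 million cells: 1.3/0.667 = 1.95 and 4.4/2.222 = 1.98.

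**Step 4: is the 100 million figure itself in doubt?** Section 6.4 provides a check: 80 mL / 2 mL/min = 40 min, and 2.5 million/min × 40 min = 100 million cells. This agrees with the Synopsis, with section 3.2 and with the closing sentence of 6.3. A dose of 200 million appears only in accounts of other studies, such as the frailty study in section 1.2.

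**Step 5: does the argument of 6.3 depend on the range?**

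- Toxicology comparison at the highest exposure (45 kg): 65/4.4 = 14.8-fold below the cited level on the printed range, and 65/2.22 = 29.3-fold below at 100 million cells. The conclusion is the same.
- Fixed dosing: the spread between the lightest and heaviest subject is 150/45 = 3.3-fold at any fixed total.

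**Step 6: does anything else use the figure?** Eligibility (sections 4.1 and 4.2) sets no body-weight limit for subjects. The infusion instructions (section 6.4 and Appendix 1) work in mL/min. The stopping guidelines (8.1.5), endpoints (2.2) and statistical analysis (section 9) contain no cells-per-kilogram quantity.

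**The case for a change.** The best case for acting is that this is the protocol's only per-kilogram statement of what its own subjects receive, that it is wrong by a factor of about two for the stated maximum, and that correcting it costs one sentence. For the 20 million pilot groups the gap is nearly tenfold (1.3/0.133 = 9.8; 4.4/0.444 = 9.9). Section 6.3 also claims support for potential efficacy as well as safety. On the printed range every subject is above 1 million/kg; at 100 million cells, subjects over 100/1.0 = 100 kg are below it, and those over 100/1.4 = 71 kg are below 1.4 million/kg.

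The arithmetic stands; the consequence does not follow from it. The protocol never makes that comparison, and it presents neither 1 nor 1.4 million/kg as a level needed for effect: they are doses used in lupus and in graft-versus-host disease. Other precedents in the same document point the other way. Section 1.5.1.2 gives 0.4 to 9 million/kg for a graft-versus-host study of 55 patients, as in 1.6.2, and 0.67 to 2.22 million/kg lies wholly inside that span. Section 1.11 gives 0.8 to 1.6 million/kg for cord-derived cells, which overlaps much of it.

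Some of the precedents need no conversion at all. The frailty study in section 1.2 gave fixed intravenous doses of 20, 100 or 200 million cells, and the COPD patients in sections 1.6.3 and 1.7 received 100 million per infusion. A reader can set 20 or 100 million cells beside those directly.

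**Conclusion.** The inconsistency is confirmed: the range in 6.3 is 1.95 to 1.98 times what the stated maximum of 100 million cells gives, and it corresponds to roughly 200 million cells, which no group receives. The range and the cell numbers in the Synopsis, 3.2, 6.3 and 6.4 contradict each other and must be reconciled by the sponsor as a matter of text. This review does not say which is right.

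No change to the plan follows. The sentence is explanatory, no one is dosed from it, and no eligibility, safety-monitoring, endpoint or analysis rule refers to it. The comparison with the 65 million/kg toxicology level and the 3.3-fold weight spread come out the same way under either range. Whoever prepares, infuses or analyses works from total cell numbers that agree wherever they appear.

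This rests on two assumptions. First, the total in the disputed sentence is meant to be this study's dose; the sentence itself gives no number, but those on either side concern this study and its maximum. Second, the cell numbers repeated across the protocol are the ones in use. If the sponsor had meant about 200 million cells, the discrepancy would lie in the treatment description and this conclusion would no longer hold; nothing in the documents points to that.
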